Determining which patients, using age and arthritic burden as predictors, can benefit from labral repair is paramount for several reasons. Showing arthroscopic repair is of little or no benefit to a specific cohort can reduce the number of unnecessary surgeries performed, increase the use of conservative therapy (if validated) and reduce the interval between diagnosis and total hip replacement. Additionally, proving a benefit exists from arthroscopic repair in a certain subset of the population will substantiate the need for developing a treatment algorithm in older patients presenting with labral tears and some degree of pre-existing arthritis. Furthermore, conservative physical therapy may prove to be of equal or greater benefit than arthroscopic repair in select patients. If true, this study will be a landmark for providing the evidence needed to recommend conservative treatment as an efficacious alternative in addition to providing a foundation for future research on this topic.

II. SPECIFIC AIMS:

Specific Aim 1: To evaluate if physical therapy alone or arthroscopic labral repair and physical therapy is of greater benefit to patients presenting at age 40 with tears of the acetabular labrum.

Hypothesis 1.1: Physical therapy will result in a significant difference in mHHS scoring at 12 months when compared to baseline.

Hypothesis 1.2: Arthroscopic labral repair will result in a significant difference in mHHS scoring at 12 months when compared to baseline.

Hypothesis 1.3: Arthroscopic labral repair and physical therapy will be superior to physical therapy alone in improving function and alleviating symptoms at 12 months when compared to baseline, as judged by the mHHS.

Hypothesis 1.4: Hypotheses 1.1-1.3 will hold true at 24 months and beyond.

Hypothesis 1.5: Functional outcome scores collected at the completion of PT will not significantly differ from those collected at 12 and 24 months and beyond in the same group.

Specific Aim 2: To evaluate the effect of arthritic burden on short term outcomes following arthroscopic labral repair.

Hypothesis 2.1: In the surgical treatment group, subjects with arthroscopically proven severe osteoarthritis (Outerbridge grade 4) will do more poorly on validated outcome measures, specifically the mHHS, after arthroscopy than subjects with less severe osteoarthritis (Outerbridge grade ≤ 3).

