The mean outcome scores of the mHHS in each treatment group at 12 months will be compared to baseline scores to assess for significant differences using paired sample t-test in SPSS 16 (SPSS, Chicago, IL). The mean outcomes scores of the mHHS between groups at 12 months will be compared using independent t-tests to assess for significant difference. We will use a Levene test to judge variance and proceed accordingly. If a statistically significant difference is detected during these analyses, we will calculate the effect size (ES) to determine how meaningful these results are outside of being statistically significant. The ES will be calculated by: [(mean mHHS score of surgical arm / mean mHHS of the conservative group) / standard deviation of the conservative group]. According to Cohen ⁵⁸, an ES <0.1 is trivial, ES of 0.1-0.3 is minimal, ES of 0.3-0.5, is moderate, and ES >0.5 is large. We will repeat the same analysis at 12 months.

Hypothesis 2.1, 2.2, and 2.3:

Diagnosis and treatment of the prearthritic and early arthritic hip has been an area of intense interest. However, our most conventional method of assessment (plain radiography) does not provide us with enough diagnostic sensitivity.⁴¹ Direct visualization on the articular surfaces in the hip is both sensitive and specific. Furthermore, emphasis is being placed on the location of arthritis as a prognostic indicator of good outcomes following hip arthroscopy. The value of arthroscopic techniques for primary

symptoms and/or prevention of OA secondary to labral tears remains unclear even though preliminary reports indicate there may be some benefit to repairing a torn labrum, even in cases of severe OA. Evaluation of arthritic change at the time of arthroscopy is important, particularly in subjects where there remains uncertainty about the efficacy of labral repair for those with articular or rim cartilage degeneration that the effects of those changes on long-term OA progression.⁵⁹

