Using the data from our retrospective review of outcomes following labral repair, a 10 point or greater difference on the mHHS as significant, and a single-tail independent t-test to evaluate the difference between means with 80% power and a 5% significance level, 35 subjects are needed to demonstrate a statistically significant difference between the average mHHS of the conservative group and surgical group. Testing of hypothesis 1.5 will be an intragroup analysis looking for a significant difference in outcome measures from the time of completion of PT (non-crossover) when compared to the same data to be collected at 12 months and 24 months. The purpose is to determine the short-term durability of the response to PT, if one is found.

70 study completers should provide us with the necessary data needed to substantiate or reject our hypothesis. There has been no prospective trial to date testing these hypotheses in the hip, but we expected a 7.3-10.3% dropout rate based on the results of a similar study in the knee. However, as of July 2018, we had 47 patients that had passed the 2-year follow-up mark, of which 5 patients were no longer in the study (combination of lost to follow-up and proceeding to total hip arthroplasty), and another 11 had yet to complete their 2-year surveys even with multiple attempts to contact them and encourage them to do so. With a yield of 31 patients out of 47, or 65.95%, we increased our sample size to 122.

Therefore, we estimate needing 122 subjects to achieve 70 study completers, in the appropriate proportion of 35 subjects per treatment arm. We enroll until reaching at least 35 subjects in each group.

The results of the MeTeOR trial in the knee show that we can expect a higher drop-out rate in the surgical group. As such, this cohort may be our limiting factor.^{40, 43, 61, 62}

Specific Aim 2. Hypotheses 2.1-2.3: *To evaluate the significance of arthritic burden on short term outcomes following arthroscopic labral repair.*

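### Aim 1 asks which treatment is better, but the 80% power belongs to a one-tailed test and the analysis section does not state sidedness; two-sided, power at 35 completers per arm is about 70%

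*Combined protocol and SAP*

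**What the plan says.** - **Section II, Specific Aim 1.** The aim is "To evaluate if physical therapy alone or arthroscopic labral repair and physical therapy is of greater benefit to patients". The same aim is repeated as the heading of the Aim 1 power analysis in Section V.
- **Section II, Hypothesis 1.3.** This is the one between-arm hypothesis for Aim 1 with a direction: "Arthroscopic labral repair and physical therapy will be superior to physical therapy alone in improving function and alleviating symptoms at 12 months".
- **Section I, Implications.** The protocol says that "conservative physical therapy may prove to be of equal or greater benefit than arthroscopic repair in select patients", and that if so the study would supply the evidence for recommending conservative treatment.
- **Section V, Power Analysis, Specific Aim 1.** For a 10-point mHHS difference, the size comes from "a single-tail independent t-test to evaluate the difference between means with 80% power and a 5% significance level, 35 subjects are needed". The following paragraphs make clear that 35 is per arm, giving 70 completers, and that 122 are to be enrolled because 31 of 47 patients (65.95%) past the two-year mark had yielded two-year data. The SD is said to come from the group's retrospective review, but its value is not given.
- **Section V, Hypothesis 1.1-1.4.** Mean mHHS "between groups at 12 months will be compared using independent t-tests to assess for significant difference". Sidedness is not stated.

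**The concern.** The question, the sizing test and the planned analysis do not match. Aim 1 can be answered in favour of either arm. A one-tailed test for surgery can return only two results: surgery superior, or surgery not shown superior. A true PT advantage falls under its null. Yet the Implications section treats such a result, at least in select patients, as one that would matter for practice.

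Because the analysis section is silent, two readings are open. Under a one-tailed analysis, half of Aim 1 cannot be answered. Under a two-tailed analysis, the 80% in the Power Analysis is not the power of the test that will be run. Leaving the choice open is also a weakness in itself. Section VIII describes an unblinded study whose team reviews all data continuously and which has no monitoring board, so the tail of the primary between-arm comparison should be fixed in writing before the outcome data are analysed.

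**Working it through.** **Inputs from the Power Analysis (Section V):** difference 10 mHHS points; alpha 5%, single tail; power 80%; 35 completers per arm; 122 enrolled; yield 31/47. The SD is not given.

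**Step 1. The plan's own figure.** Without an SD, 35 per arm cannot be computed forward, so I solve for the SD that makes the statement true. With n = 2(z₁₋α + z₁₋β)²·SD²/Δ², the standardised difference is d = (1.645 + 0.842)·√(2/35) = 0.594, and SD = 10/0.594 = 16.8. The exact calculation (noncentral t) gives d = 0.600 and SD = 16.7. SDs for which the required n rounds up to exactly 35 run from 16.4 to 16.8 across the two methods. The SD is therefore an assumption, but the stated n, alpha and power fix d, and the power below depends only on d and n.

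**Step 2. The same design tested two-sided at 5%.** Power ≈ Φ(d·√(n/2) − 1.960). At n = 35: 0.594 × √17.5 = 2.487; 2.487 − 1.960 = 0.527; Φ(0.527) = 70.1%. The exact figure is 69.7%. Over all SDs that round to 35 per arm, the range is 69.7% to 71.3%.

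**Step 3. Other numbers of completers** (equal arms, same d):

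| Completion assumption | Completers per arm | Two-sided 5% power |
|---|---|---|
| Planned minimum | 35 | about 70% |
| 122 × 31/47 = 80.5 in total | about 40 | about 75% (exact 75.5%) |
| 90 of 122, i.e. 74% | 45 | about 80% (exact 80.4%) |
| 122 × 42/47 = 109 in total (only the 5 who had left are lost) | about 54 | about 87% |

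At 35 per arm, the difference detectable with 80% two-sided power is about 11.3 points rather than 10.

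**Step 4. The one-tailed test when PT is better.** If PT were truly 10 points better, a one-tailed test for surgery would reject with probability Φ(−1.645 − 2.487) = Φ(−4.13), about 0.00002. Any one-sided test behaves this way in the opposite direction. The protocol does not project such an effect.

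**Step 5. Could 35 per arm already be a two-sided number?** It could if the SD were about 14.7 (exact) or 14.9 (normal approximation). The text says single-tail, however, so the stated calculation is not that one. Publishing the SD would settle the matter.

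**The case against.** **A directional test has some basis here.** Hypothesis 1.3 is prespecified and favours surgery, and the group's retrospective comparison (Section I, Preliminary Data) found a non-significant tendency toward worse outcome without surgery. This explains a one-tailed calculation for Hypothesis 1.3. It does not justify one for Aim 1, which is unqualified and heads the same power analysis, and the protocol offers no justification.

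**A reader might infer that the trial can never declare PT better.** The documents do not support that. The single tail appears only in the sample-size basis, where its direction is not named and has to be inferred from Hypothesis 1.3. The analysis section's wording, "will be compared using independent t-tests to assess for significant difference", would allow a two-sided test. What stands is that the sizing test cannot declare a PT advantage and that the analysis test is not specified.

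**A reader might take about 70% as the power the trial will have.** It is the power at the planned minimum. The plan enrols 122, and the 65.95% yield is a two-year figure in which 11 of the 16 missing patients had still to return surveys. No 12-month completion figure is given, and better 12-month completion could bring two-sided power to 80% or above. Against that, the plan removes patients with unexpected pathology at arthroscopy, expects higher dropout in the surgical arm, and words its enrolment target as at least 35 per group. A range with its assumptions is the honest statement.

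**A reader might take the Implications section as predicting that PT will win.** The sentence reads "conservative physical therapy may prove to be of equal or greater benefit than arthroscopic repair in select patients", so it covers equality as well as advantage and is limited to select patients. A two-sided superiority test does not establish equality, and the fix below does not claim that it does.

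**Conclusion.** The concern holds in this form: the 80% power is stated for a one-tailed test that cannot answer Aim 1 in both directions, no justification is given, and the analysis section leaves sidedness open. For a two-sided 5% test of a 10-point difference, power is about 70% at 35 completers per arm and about 75% at 40 per arm, and it reaches 80% only at about 45 per arm. These figures rest on d of about 0.60, back-solved from the plan's own n, alpha and power, on equal arms, and on the completion rate named for each. The implied SD of about 16.7 is an assumption until the sponsor gives the value used. The treatments, the data collected and the estimated between-arm difference are not affected; the fault lies in how the primary between-arm test and its power are specified.

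**What to change.** 1. In Section V, both under Hypothesis 1.1-1.4 and in the Power Analysis for Aim 1, state that the between-arm mHHS comparison is two-sided at the 5% level and reported with a two-sided 95% confidence interval, so that an advantage of either treatment can be declared.
2. Give the SD taken from the retrospective review.
3. Restate the power for 10 points as about 70% at 35 completers per arm and about 75% at 40 per arm (122 enrolled at the 65.95% two-year yield), naming the completion assumption. Update these figures if the disclosed SD differs from about 16.7.
4. Do not present a non-significant two-sided result as evidence that the treatments are equal.

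The cost is a few sentences and a less favourable stated power. No change in enrolment is asked for. For information, 80% two-sided power would need about 90 completers, or about 137 enrolled at the 31/47 yield (90 ÷ 0.6596 = 136.5).

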Hypothesis 2.2: Cartilage defects at or near the chondrolabral junction are prognostic indicators of worse outcomes as determined by the mHHS.

Hypothesis 2.3: Subjects with any degree of joint space narrowing (classified by Tonnis and Kellgren-Lawrence grading, see below) on plain radiographs will have more pain, regain less function, and do more poorly based on validated outcome measures, specifically the mHHS, at 6 and 12 months than subjects without any degree of joint space narrowing on plain radiographs.

EXPLORATORY Specific Aim 3: To evaluate the relationship between joint space narrowing on plain radiography and arthroscopically proven osteoarthritis.

Hypothesis 3.1: Tonnis grading and Kellgren-Lawrence grading on plain radiography are not predictive of the severity of arthritis at the time of arthroscopy.

Specific Aim 4: To analyze the data of subjects crossing over from PT alone to PT and surgery.

Hypothesis 4.1: Primary outcome scoring (mHHS) at 12 and 24 months after cross to surgery and PT will differ significantly from those initially randomized to surgical treatment.

Hypothesis 4.2: Baseline scores on outcome measures of those subjects crossing over will not differ significantly from those obtained at the time of crossover.

III. SUBJECT SELECTION & ENROLLMENT:

Study Overview: This is a prospective randomized control trial (RCT), which will enroll subjects with a clinically diagnosed tear of the acetabular labrum. Subjects who have been diagnosed with a labral tear in clinic will receive conservative physical therapy treatment alone or arthroscopic surgical labral repair and physical therapy. If it is discovered that there is unexpected pathology at the time of arthroscopy for subjects in the surgery group, those subjects will be removed from the study. This is due to the possibility that the source of pain is less likely a result of the dysfunction of the labrum and more likely due to aberrant extra-articular biology. We will use validated outcomes measures that include the mHHS, LEFS, HOS, NAHS, and iHOT-33 (see below) and review the medical record for physical exam findings to track patient progress throughout their involvement in the study which will continue for as long as they are a patient of the PI. Study procedures will be complete when the last enrolled subject completes 24-month follow-up and completes the corresponding surveys.

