In order to objectively track each individual subject's progress enrolled in the PT alone group, we employ the use of "advancement criteria". These criteria will serve as a safety and quality control measure. Failure to meet these advancement criteria is a trigger for re-referral back to the orthopedic surgeon for potential cross over due to an inadequate response to PT. Non-achievement of the advancement criteria outlined for each phase of the physical therapy protocol is a cause for clinical concern that the PT intervention has been ineffective or not effective enough. We plan to use these advancement criteria for those subjects enrolled in the physical therapy alone arm of this randomized controlled trial as an objective measure to monitor subject progress and safety. At each treatment session, which will ideally take place every third day (1-2x/week) once enrolled, subjects will undergo complete evaluation by the physical therapist for clinical concern that the subject is not adequately responding to PT (page of the detailed protocol). Therefore, each subject who is compliant with the non-operative PT protocol will undergo formal evaluation at least once per week during the course of treatment. This is exactly what would be done in normal routine practice and our study procedures will not deviate from this. Progression through the advancement criteria will be documented in the subjects chart on a separate sheet of paper (attached) requiring the dating and signature of the physical therapist for advancement through the protocol or re-referral back to the surgeon, which is considered standard of care and common practice.

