In addition, subjects can subjectively withdraw from PT any time point if they feel that it is not working for them the way they would like. However, in order to standardize the amount of time that lapses between enrollment and potential cross-over, subjects wishing to transition to surgical treatment cannot do so until 6 weeks after initial enrollment (see figure 5 of the study schema). There are several reasons for this: First, we want subjects to have enough time to see the benefits of PT, as they may not be immediate. Second, if the decision to cross over is made prior to 6 weeks, the remaining time allows for scheduling of a follow-up appointment in a timely manner that does not delay appropriate patient care. Lastly, subjects are not required to continue under the PT protocol, they can stop at any point and not receive further PT or medically directed care until their follow-up. This scenario is no different than if a patient, in a non-study setting, self discontinued a recommended course of PT and sought surgical consultation elsewhere. The advantage here is that subjects will already be known to both the hospital system and surgeon, which allows for quicker consultation.

SURGERY

While randomization is a research procedure for this study, the surgery itself is not a research procedure. This surgery is standard of care for patients with symptomatic labral tears, and the PI regularly performs labral repair in patients not enrolled in research.

POSTOPERATIVE PROTOCOL

All procedures are performed on an outpatient basis. Patients are allowed flat-foot full weight bearing immediately postoperatively. Patients are instructed in gait training, keeping a level pelvis and avoiding any lurching of their pelvis during ambulation. Patients are kept weight bearing as tolerated with crutches for 6 weeks postoperatively for a labral repair. Patients are allowed full active range of motion as tolerated immediately with avoidance of deep squatting and impact loading exercises for 4 months postoperatively. This is considered standard practice.

V. BIOSTATISTICAL ANALYSIS

Hypothesis 1.1-1.4:

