1. The study staff will meet regularly with [name] to review study participants and the data that has been collected on them to date. If a subject becomes disqualified or must leave the study for safety concerns, [name] will personally inform them of the situation through the subjects preferred method of contact. [name] will be leading and administering the conservative arm of the study (subjects being treated non-surgically with physical therapy and subjects in the post-operative period receiving rehabilitative physical therapy). She will inform [name] of patient progress and any potential clinically significant events that may warrant further discussion and could ultimately result in the dismissal of a patient from the study.
 - a. As this is a prospective study comparing the gold standard of treatment (labral repair) to a potentially equivalent therapeutic modality, qualifying subjects will never be denied the option to undergo labral repair via hip arthroscopy. The treatment schema allows for subjects in the non-surgical arm (physical therapy alone) to cross over to the surgical treatment group at any time (following physical therapy) from initial enrollment if they wish to do so. Subjects who decide to crossover or are indicated to crossover through the non achievement of advancement criteria will have the PT discontinued at that time point but must wait for official crossover at 6 weeks after initial enrollment. Participants can always decide to leave the study if this is not what they want. The decision to cross over will in no way affect the quality of healthcare current or prior study participants receive. All of this will also be explained to them during the consent.
 - b. We will review all data continuously and should there be a obvious clinical detriment to specific treatment arm such as repeated poor outcomes or worsening function, further investigation will be initiated to determine if this is an isolated occurrence or if there is a significant trend which warrants cessation of study protocol and disenrollment of subjects.
 - i. Stopping rules include a clear difference in morbidity, as measured by interval physical exams and outcomes questionnaires, between treatment groups
 - ii. Any significant mortality possibly linked to study procedures will result in immediate suspension of the study protocol.

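### Hypothesis 1.5 has no sound rule for PT completers who later cross over to surgery, so its durability test leans towards finding a lasting response

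*Combined protocol and SAP*

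**What the plan says.** Hypothesis 1.5 (section II) is a hypothesis of no change within the PT group: "Functional outcome scores collected at the completion of PT will not significantly differ from those collected at 12 and 24 months and beyond". Section V, Power Analysis, adds: "Testing of hypothesis 1.5 will be an intragroup analysis looking for a significant difference in outcome measures". The comparison runs "from the time of completion of PT (non-crossover") to 12 and 24 months, and the aim is given as follows: "The purpose is to determine the short-term durability of the response to PT, if one is found". No margin, sample size or power is stated for this hypothesis, and no rule covers subjects who finish PT and cross over afterwards.

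The routes to crossover are described elsewhere:

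- Section IV, Physical Therapy Visits: failing the advancement criteria leads to "re-referral back to the orthopedic surgeon for potential cross over due to an inadequate response to PT".
- Same section: "subjects can subjectively withdraw from PT any time point if they feel that it is not working for them". Crossover opens six weeks after enrolment, and PT sessions may run to 12 weeks.
- Section VIII, item 1a: the PT-alone arm may choose "to cross over to the surgical treatment group at any time", qualified as following physical therapy. No last date is given.

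Aim 4 treats crossovers separately. Hypothesis 4.1 compares their post-surgery scores with those of subjects randomized to surgery. Hypothesis 4.2 reads: "Baseline scores on outcome measures of those subjects crossing over will not differ significantly from those obtained at the time of crossover". Neither uses the completion-of-PT score.

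**The concern.** A subject can finish PT with a good score, lose the benefit, and then have surgery. That is the event a durability analysis exists to detect. If such subjects leave the analysis, the sample is selected on the later course of the outcome being measured, and the remaining scores can look stable while the PT completers as a whole decline. If they stay in with post-surgery scores, any benefit of surgery is credited to PT.

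The form of the test adds to this. Hypothesis 1.5 is supported by a non-significant result with no margin, so a smaller observed decline and a smaller sample both work in its favour. Section I (Implications) hopes the study can support recommending conservative treatment, and a claim of lasting benefit would be part of that case.

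**Working it through.** **1. The plan's own figure.** No number is given for Hypothesis 1.5. The nearest is 35 per arm for the between-group comparison (10 points, one-sided 5%, 80% power). The SD is not stated, so 35 cannot be reproduced, but the SD it implies can be found:

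SD = 10 / [√(2/35) × (1.645 + 0.842)] = 16.8 (normal approximation; 16.7 with the t-test).

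I use 16.8 as an assumed SD of within-person change. This follows if the SD at each time is 16.8 and the correlation between the two times is 0.5, since SD of change = 16.8 × √(2 × (1 − 0.5)) = 16.8.

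**2. Who is affected.** Those who cross over between six weeks and the end of PT have no completion score and no completed response to lose, so leaving them out fits the stated purpose. Only PT completers who cross over later matter. Call their share of PT completers f.

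**3. Bias if late crossovers are excluded.** Let S be the mean change in stayers and C the mean change that late crossovers would have shown on PT alone. All completers average (1 − f)S + fC, so stayers alone are too favourable by

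S − [(1 − f)S + fC] = f × (S − C).

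Shift in points, with f and the gap S − C both assumed:

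| f | gap 5 | gap 10 | gap 15 | gap 20 |
|---|---|---|---|---|
| 10% | 0.5 | 1.0 | 1.5 | 2.0 |
| 20% | 1.0 | 2.0 | 3.0 | 4.0 |
| 30% | 1.5 | 3.0 | 4.5 | 6.0 |
| 40% | 2.0 | 4.0 | 6.0 | 8.0 |

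**4. Effect on the test (illustration).** Assume 35 PT completers, SD of change 16.8, a true mean change of −8 on PT alone, and a tendency to cross over that correlates 0.5 with decline. A two-sided paired t-test at 5%, simulated 3,000 times per scenario, is non-significant in about 22% of runs when all 35 are analysed. After exclusions:

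| Late crossover | Mean change seen | Non-significant | Same number removed at random |
|---|---|---|---|
| 10% | −6.2 | 46% | 27% |
| 20% | −5.1 | 62% | 32% |
| 30% | −4.1 | 75% | 36% |
| 40% | −2.8 | 86% | 45% |

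Most of the rise is selection, not loss of numbers.

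**5. Bias if late crossovers stay in with post-surgery scores.** With the same assumptions and a 15-point gain from surgery (assumed), 20% late crossover gives a mean change of −5.0 and 56% non-significant results, against 23% when all subjects contribute PT-only scores. The distortion is close to that of exclusion. If surgery gave no gain, it would disappear.

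**6. Power.** With the same SD, the power to detect a 5-point decline is 40% with 35 pairs and 25% with 21 pairs. A non-significant result is weak evidence of durability even without selection.

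**The case against.** The best defence is that the parenthesis directly follows the words about completing PT, so it may only define the starting sample: subjects not crossed over by then. Hypothesis 1.5 in section II names the PT group with no exclusion. A reader might infer that the plan certainly removes everyone whose response faded; the text does not settle that. This changes the mechanism. The direction stays the same if surgery helps.

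Second, the crossover route described in detail operates during PT, and those subjects are properly outside a durability question. A reader might count all crossovers as lost responders, but the protocol does not support that. It also says less about why subjects cross over after PT. That these are mainly people whose benefit faded is a reasonable inference from the stated triggers, not a documented fact.

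Third, the size rests on assumptions. It is tempting to say that a true 5-point fall would all but vanish, since 20-30% crossover with correlations of 0.5-0.7 gives shifts of about 2 to 6 points. Those inputs are not in the documents. At 10% late crossover and a correlation of 0.2, the truncated-normal formula gives 0.2 × 16.8 × 0.1755 / 0.90 = 0.7 points.

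Finally, durability among those who remain on PT alone is a legitimate conditional question, and the restriction is disclosed. That stands, provided the result is labelled as such. Aim 4 does not fill the gap, because neither of its hypotheses measures change from completion of PT.

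**Conclusion.** The concern holds for PT completers who cross over later. On one reading they are excluded, and on the other they contribute post-surgery scores. The first biases Hypothesis 1.5 towards a durable response if late crossovers decline more than stayers, as the stated triggers suggest. The second does so if surgery helps.

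The size cannot be determined from the documents. Under the assumed ranges (10-40% late crossover, a 5-20 point gap) it is about 0.5 to 8 points of mean change. The low end would hardly matter; the high end could hide a real decline.

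A reader might extend this to the main result of the trial. That would be wrong: Hypothesis 1.5 is a secondary within-arm question, and the point leaves the primary between-group comparison untouched.

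**What to change.** - Define the Hypothesis 1.5 population as all PT-arm subjects with a completion-of-PT score, and state what the parenthesis means.
- Do not use post-surgery scores as outcomes for durability of PT.
- Report the proportion who keep their response at 12 and 24 months, counting later crossover or hip replacement as loss of response. Prespecify and justify the within-person threshold. The 10 points in the Power Analysis is a between-group difference and does not justify one by itself.
- Report the number and timing of late crossovers.
- Keep the non-crossover paired comparison, labelled as conditional on staying with PT alone.
- As a sensitivity analysis, use the last score before crossover, such as the one Hypothesis 4.2 needs.

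**Cost.** This is mainly analysis wording, with no extra subjects. Section IV schedules surveys around normal clinic visits and does not describe a survey at crossover, so the team should confirm that this score is collected. The durability estimate will be less favourable. Pre-crossover scores are taken at variable times, when symptoms are prompting surgery, and may overstate decline; that is why they belong in a sensitivity analysis.
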